For participants who permanently discontinue from study treatment **and who decline continued study participation**, an Early Termination (ET) Visit will be scheduled as soon as possible followed by an EOS Visit approximately 35 days later. The ET Visit procedures are identical to the End of Treatment (EOT) Visit procedures. If the discontinuation occurs at a specific onsite visit, this visit will become the ET Visit and EOT Visit procedures should be followed. Participants who withdraw consent to all follow-up will be asked about the reason(s) and will be assessed for the presence of any AEs.

If premature withdrawal from the study occurs for any reason, the Investigator must determine the primary reason for a participant's premature withdrawal from the study and record this information in the medical records and on the electronic case report form (eCRF).

Withdrawn participants will not be replaced.

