7.1 Lipid Profile/Biomarkers

Samples will be collected for the lipid profile/biomarkers at visits specified in the Schedule of Procedures ([Appendix A](#)). The lipid profile/biomarker samples will be analyzed for ApoB, HDL-C, LDL-C, non-HDL-C, TC, and TG. Samples should be collected while the participant is fasting (a minimum of 8 hours).

At Baseline (Visit 2), Day 84 (Visit 4), and Day 365 (Visit 7)/EOT/ET, LDL-C will be measured for all participants by preparative ultracentrifugation, also referred to as beta quantification. At all other scheduled visits, LDL-C will be calculated using the Friedewald equation unless $TG \geq 400 \text{ mg/dL} (\geq 4.52 \text{ mmol/L})$ or $LDL-C \leq 50 \text{ mg/dL} (\leq 1.30 \text{ mmol/L})$. If $TG \geq 400 \text{ mg/dL} (\geq 4.52 \text{ mmol/L})$ or $LDL-C \leq 50 \text{ mg/dL} (\leq 1.30 \text{ mmol/L})$, then LDL-C level will be measured directly by preparative ultracentrifugation.

All lipid profile/biomarker values will be blinded during the study through the EOS Visit (Visit 8). Participants, the Sponsor, Investigators, and all study site personnel involved in the study, including personnel carrying out study procedures, evaluating participants, entering study data, and/or evaluating study data, will remain blinded to lipid profile/biomarker values until all participants have completed the EOS Visit and the database has been locked for analysis.

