3.1.2 Analysis Visits

Scheduled visits will be assigned to analysis visits as recorded on the CRF.

For each analysis visit, if a scheduled visit occurs within the analysis day window, then the measurement from this scheduled visit will be used. If no scheduled visit occurs or laboratory results of the scheduled visit were unreportable, the unscheduled measurement closest to the target day will be used. If measurements are equidistant to the target day, the latter will be used. Otherwise, unscheduled visits will not be re-assigned and will remain labelled as unscheduled. If laboratory measurements for the scheduled visit were taken while a participant was not in a fasting state and laboratory measurements are available from an unscheduled visit during which the participant was in a fasting state (and the visit occurred within seven days of the scheduled visit), those fasted labs will be utilized in place of the unfasted labs.

Early termination (ET) visits will be assigned to analysis visits according to the following visit windows in Table 2:

Table 2 Analysis Visit Windows

Analysis Visit	Target Analysis Day	Low Analysis Day	High Analysis Day
Day 1 (Visit 2)	1	NA	NA
Day 30 (Visit 3)	30	2	57
Day 84 (Visit 4)	84	58	132
Day 180 (Visit 5)	180	133	225

Day 270 (Visit 6)	270	226	317
Day 365 (EOT)/(Visit 7)	365	318	N/A

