3.1.4 Definition of Baseline

Baseline is defined as the last measurement prior to the first dose of study drug, unless otherwise stated.

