Supplemental analyses will be performed for the primary efficacy endpoint in order to assess any differences with the results from the primary analysis and investigate what effect, if any, protocol violations have on the trial results. In the first supplemental analysis, a mixed model for repeated measures (MMRM) approach will be utilized. The LDL-C values measured by preparative ultracentrifugation will be used. The analysis will include fixed effects for treatment group, visit, and treatment-by-visit interaction, along with covariates of the Baseline LDL-C value as a continuous covariate. The restricted maximum likelihood estimation approach will be used with an unstructured covariance matrix. The LS mean, standard errors, and 2-sided 95% confidence intervals for the treatment group and for the comparison of the treatment group to the placebo group will be provided. The MMRM approach will include all available assessments of percent change in LDL-C from Day 1, Day 30, Day 84, Day 180, Day 270, and Day 365. The model assumes that the data are missing at random (MAR). For missing data, the model will use all information from the other time points to estimate the mean treatment difference at the given time point. No imputation of missing data will be performed. The analysis will be conducted for ITT Population.

The analysis will be implemented using SAS® Proc Mixed. The sample SAS code can be found below:

.....

Note:

USUBJID = unique participant identifier
TREATMENT = 0 (Placebo), 1 (Obicetrapib)
VISIT = visit
LDLC_BASE = Baseline LDL_C value
PCHG = Percent change from Baseline

```
proc mixed;
  class USUBJID TREATMENT VISIT CVRISK STATIN;
  model PCHG = TREATMENT LDLC_BASE VISIT TREATMENT*VISIT / solution cl;
  Repeated VISIT / TYPE=UN sub=USUBJID;
  lsmeans VISIT*TREATMENT / cl diff;
run;
```

Additional supplementary analysis will be performed using the ANCOVA model from the primary analysis based on the FAS, mITT, mITT On-Treatment, and PP populations. No imputation for missing data will be performed for the analysis.

Secondary Estimand

A secondary estimand will be assessed for the primary efficacy endpoint. The secondary estimand is defined by the following key attributes:

- **Treatment:** obicetrapib versus placebo
- **Target Population:** participants who are randomized into the study
- **Analysis Population:** The ITT Population
- **Intercurrent events:** treatment discontinuation, prohibited medication use

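### The supplemental MMRM, also the template for the hypothetical estimand, cannot be fitted as written: Day 1 is a response visit, ultracentrifugation LDL-C is needed where it is rarely run, and the estimand's inclusion rule contradicts itself

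*SAP*

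**What the plan says.** **The model.** SAP 3.4.1 (Supplemental Analyses) describes an MMRM in the ITT Population, fitted by restricted maximum likelihood with an unstructured covariance under missing at random. On the LDL-C source: "The LDL-C values measured by preparative ultracentrifugation will be used". The responses will "include all available assessments of percent change in LDL-C from Day 1, Day 30, Day 84, Day 180, Day 270, and Day 365". The sample code has "model PCHG = TREATMENT LDLC_BASE VISIT TREATMENT*VISIT / solution cl", with no filter on visit, and requests treatment contrasts at every visit. For a missing value, "the model will use all information from the other time points".

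**Baseline.** SAP 3.1.4: "Baseline is defined as the last measurement prior to the first dose of study drug". Protocol 7.1 takes the Baseline PUC sample at Visit 2, which is Day 1.

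**Where PUC exists.** Protocol 7.1 runs PUC in all participants only at Baseline, Day 84 and Day 365/EOT/ET. "At all other scheduled visits, LDL-C will be calculated using the Friedewald equation unless" triglycerides are 400 mg/dL or more or LDL-C is 50 mg/dL or less; only then is PUC run. There is one further route. SAP 3.1.2 says "Early termination (ET) visits will be assigned to analysis visits according to the following visit windows", so an early termination PUC sample on Days 2–57, 133–225 or 226–317 counts as Day 30, 180 or 270.

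**Secondary estimand.** SAP 3.4.1 uses a similar MMRM for the hypothetical estimand. Its handling attribute repeats the inclusion sentence of the treatment-policy estimand: every available Baseline and Day 84 value enters. The paragraph after it treats values obtained after stopping study drug or taking prohibited medication as excluded.

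**Related rules.** SAP 3.4.2 gives a Friedewald-unless-PUC rule for Day 180 LDL-C as a secondary endpoint. SAP 3.4.1 (Primary Analysis) repeats the primary-endpoint analyses with Friedewald and Martin-Hopkins values.

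**The concern.** A response level that is constant by definition cannot sit in an unstructured covariance model. A model that accepts only PUC values has almost none at three of its five post-baseline visits, and those it has exist largely because LDL-C was already low. That conflicts with the missing-at-random assumption and with the promise to borrow from other visits.

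At stake are the first supplemental analysis of the primary endpoint and the only model named for the secondary estimand. For that estimand, the conflicting inclusion rule concerns the feature that separates it from the primary one: whether Day 84 values after an intercurrent event count.

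**Working it through.** **1. The plan's own design figure.** Protocol 9.2.5 and SAP 2.2.2 give 300 participants, 5% dropout, a 30-point effect, SD 15 and one-sided 0.025. 300 × 0.95 = 285, or 190 and 95 at 2:1. SE = 15 × √(1/95 + 1/190) = 1.885, and 30 / 1.885 = 15.9. Power is above 99.99%, consistent with the stated more than 90%. The point does not rest on this figure.

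**2. Day 1.** Percent change at Day 1 = 100 × (Day 1 − Baseline) / Baseline = 0 for everyone with a Day 1 value, by any LDL-C method. The code has one Baseline slope for all visits, so Day 1 is fitted exactly when that slope is 0. Its variance can then shrink without limit, and −2 log-likelihood falls by N × ln(10) for each tenfold cut: 285 × 2.3026 = 656.

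A numerical check used 300 simulated participants with a true slope of −0.05. It profiled −2 log-likelihood (up to a constant) over the common slope:

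| Slope | With Day 1 | Without Day 1 |
|---|---|---|
| −0.05 | 7856.9 | 7450.1 |
| −0.001 | 5509.7 | 7456.4 |
| −1e-6 | 1365.0 | 7456.6 |
| −1e-8 | −1398.1 | 7456.6 |

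The last step with Day 1 is a 10,000-fold variance cut: 4 × 300 × 2.3026 = 2763.1, matching 1365.0 + 1398.1. Without Day 1 there is an ordinary minimum near −0.05. The check used maximum likelihood; the argument carries over to REML.

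**3. PUC counts at Days 30, 180 and 270.** The documents give no Baseline LDL-C distribution. Assumed: log-normal, truncated at the 70 mg/dL entry limit, median 115, log-SD 0.35, and triglycerides ≥400 mg/dL in 0–1%. Effect and SD are the plan's. The share with LDL-C ≤50 mg/dL is then 8.54% on obicetrapib and 0.16% on placebo.

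- Obicetrapib: 0.0854 × 190 = 16.2. With 1% triggered by triglycerides, add 0.01 × (190 − 16.2) = 1.7, giving 17.9.
- Placebo: 0.0016 × 95 = 0.15. With 1% triggered by triglycerides, add about 0.95, giving 1.10. Simulated values run from 0.1 to 1.2.

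With median 90–140 and log-SD 0.25–0.35, the LDL-C trigger alone gives 3.2–17.0% on obicetrapib and 0.03–0.36% on placebo.

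**4. Empty placebo cells.** Treating the three visits as independent, P(at least one empty) ≈ 1 − (1 − e^−λ)³, with λ the expected placebo count per visit. At λ = 1.10 this is 1 − 0.667³ = 0.70; at λ = 0.15 it is 1 − 0.139³ = 0.997. Simulation with a within-person correlation of 0.6 gives about 0.98 at the low-count end, hence roughly 70–98%. An empty cell makes that visit's contrast not estimable. This depends on the assumptions: at SD 25 the chance falls to 4–51%. Where no cell is empty, the few values present are still selected on the outcome.

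**5. Day 84.** In 60 simulated trials of 300 (true effect −30, random 5% dropout, Day 1 removed), the Day 84 estimate averaged:

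- selective PUC kept at Days 30/180/270: −29.92 (SD 1.66)
- PUC at Days 84 and 365 only: −29.89 (SD 1.65)
- all five visits filled, method differences not modelled: −29.88 (SD 1.69)

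**6. The estimand text.** One sentence admits all Day 84 values; the next paragraph removes those after an intercurrent event. For scale only: if a share s of obicetrapib participants stop before Day 84, are still measured, and lose a fraction f of the effect, inclusion moves the estimate by 30 × s × f. For s = 2–10% and f = 0.5–1 that is 0.3 to 3.0 points. Both inputs are assumed. The plan's 5% dropout describes non-evaluable participants, a different group.

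**The case against.** - **Day 1 reveals itself.** The failure shows at the first run and cannot silently give a wrong estimate. The code is labelled a sample, it lists CVRISK and STATIN as class variables without using them, and detailed programming specifications are kept separately. This lowers the risk of harm, but the SAP text itself lists Day 1, and the repair belongs there before unblinding.
- **Missing PUC is foreseen.** SAP 3.4.1 treats an absent PUC value as missing, and the Friedewald and Martin-Hopkins repeats would fill every post-baseline visit. That stands as mitigation. It does not repair the PUC model that the text puts first, and the repeats carry the same Day 1 defect.
- **The hypothetical intent is clear.** The strategy's name and its explanatory paragraph both point to exclusion. That is so; the attribute still says the opposite and needs correcting.

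Three stronger readings are tempting. A reader might put a bias figure on the Day 30, 180 and 270 contrasts. The documents do not support one: its size changes with the simulation set-up, its sign turns on an undocumented share with high triglycerides, and at the real sample size the contrast will often not exist. A reader might also infer that the primary result or Type I error is at risk; neither depends on this model. Finally, Protocol 4.3 says "If the discontinuation occurs at a specific onsite visit, this visit will become the ET Visit and EOT Visit procedures should be followed", from which one might infer a general ambiguity about samples at the discontinuation visit. That rule concerns participants who also decline further participation; others keep their scheduled visits, and the SAP excludes only later values. It is a narrow edge case and not part of this point.

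**Conclusion.** The point holds as a defect of specification that should be fixed. The Day 1 problem follows from the definitions and needs no assumption. The mismatch between the required PUC values and the protocol's sampling is equally plain, and availability that depends on the current value contradicts the stated missing-at-random assumption. The counts and the 70–98% probability rest on the assumed Baseline distribution, SD 15 and the triglyceride share. The supported conclusion is that the interim contrasts are not estimable or not meaningful.

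The reach is limited. With Day 1 removed, Day 84 stays within about 0.1 points of the truth in the simulation under random dropout. What is lost is the help Day 30 should give for a missing or excluded Day 84 value, so the hypothetical estimand would rest close to complete cases.

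**What to change.** 1. Delete Day 1 as a response level in every MMRM version, including the Friedewald and Martin-Hopkins repeats. Keep Baseline LDL-C as the covariate.
2. State the LDL-C source by visit, and apply the same rule to the secondary-estimand MMRM. Either:
   - keep PUC at Baseline, Day 84 and Day 365, and at Days 30, 180 and 270 use the Friedewald-unless-PUC rule of SAP 3.4.2, with percent change there taken from a Baseline by the same method; or
   - limit the PUC MMRM to Days 84 and 365, and name the Friedewald-unless-PUC repeat as the all-visit MMRM.
3. Reword the secondary estimand's handling attribute so that values after treatment discontinuation or prohibited medication use are excluded, matching its next paragraph.

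The cost is SAP wording; no new data are needed. The first option in step 2 mixes LDL-C methods between visits; the second leaves Day 30 information unused.

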2.2 Study Design

2.2.1 *Overview*

This study is a multisite, placebo-controlled, double-blind, randomized Phase 3 study in approximately 300 participants with a history of HeFH who are not adequately controlled by their lipid-modifying therapy to evaluate the efficacy, safety, and tolerability of obicetrapib.

Approximately 300 eligible participants will be randomized in a 2:1 ratio, respectively, to the

following treatment groups:

- Obicetrapib group: one 10 mg obicetrapib tablet once daily; or
- Placebo group: 1 placebo tablet once daily.

At least 70% of the participants enrolled into this study must be taking high intensity statins (HISs). HeFH diagnosis is defined by existing confirmation via genetic testing, WHO Criteria/Dutch Lipid Clinical Network (DLCN) Criteria with a score of >8 points, and/or Simon Broome Register Diagnostic Criteria [1,2].

Starting on Day 1, each participant will self-administer their assigned study drug once daily until Day 365. During the Treatment Period, participants will return to the study site for efficacy and safety assessments. Blood samples for pharmacokinetic (PK) assessment will be collected at specified visits throughout the study. The End Of Study (EOS) Visit will be conducted approximately 35 days after the participant's last dose of study drug, during which vital signs; limited serum chemistry, hematology, and coagulation parameters; pharmacokinetics; concomitant medications; and AEs will be assessed.

The study drug blind will be maintained through the EOS Visit (Visit 8). Participants, the Sponsor, Investigators, and all study site personnel involved in the study, including personnel carrying out study procedures, evaluating participants, entering study data, and/or evaluating study data, will remain blinded to treatment allocations until all participants have completed the EOS Visit assessments and the database has been locked for analysis.

Active and placebo products will be identical. Medication bottles with a unique code will be assigned to participants at various points in the study by the Medpace Interactive Response Technology system.

Refer to [Table 1 Schedule of Procedures](#) for a complete list of procedures to be completed at each study visit.

Table 1 Schedule of Procedures

Visit	Screening		Treatment Period					EOS
	V1	V2	V3	V4	V5	V6	V7/EOT/ET ¹	
Study Day	-14 to -1	1	30	84	180	270	365	35 days after last dose
Window (±days)	±3		±3	±7	±7	±7	±7	±7
Informed consent	X							

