7. A single 12-lead ECG will be performed in the supine position after 10 minutes of rest.
8. Participants must fast for a minimum of 8 hours prior to samples being collected.
9. Samples should be collected prior to study drug administration.
10. Urinalysis will be performed locally by dipstick analyses from a sample of mid-stream urine. In case of abnormal results, microscopy and other assessments will be performed at the local laboratory and the abnormality recorded as an AE.
11. A PK sample will be collected prior to study drug administration for trough measurement of obicetrapib in plasma. At Visits 2, 5, and 7, participants should take study drug after a trough PK sample has been drawn.
12. The PK sample at Visit 4 is not designated in the protocol, however the PK will be assessed using residual serum from the Day 84 limited chemistry panel to confirm patients are taking IP.

AE = adverse event; ApoA1 = apolipoprotein A1; BMI = body mass index; CV = cardiovascular; ECG = electrocardiogram; EOS = End of Study; EOT = End of Treatment; ET = Early Termination; FSH = follicle-stimulating hormone; hsCRP = high sensitivity C-reactive protein; Lp(a) = lipoprotein (a); PK = pharmacokinetic(s); TSH = thyroid-stimulating hormone; UACR = urine albumin-creatinine ratio; UPCR = urine protein-creatinine ratio; V = Visit.

2.2.2 *Sample Size Determination*

Enrollment of approximately 300 participants globally is planned for this study.

Assuming an approximate 5% drop out rate, approximately 285 participants will be evaluable for efficacy. This sample size of at least 285 evaluable participants will provide more than 90% power to detect a 30% reduction of LDL-C (standard deviation 15%) levels in the obicetrapib group compared to the placebo group at a 1-sided significance level of 0.025. This sample size will also contribute to sufficient participant exposure and safety data.

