3.4.1 Primary Efficacy Endpoints

Primary Analysis

The primary efficacy endpoint is the percentage change from Baseline to Day 84 in LDL-C in the obicetrapib group compared to placebo group.

The LDL-C values measured by preparative ultracentrifugation (PUC) will be used. If the latter is not available, the LDL-C values will be assumed missing.

All the analysis for primary efficacy endpoint will be repeated with LDL-C values calculated as follows:

1. LDL-C will be calculated using the Friedewald equation unless triglycerides ≥ 400 mg/dL or LDL-C ≤ 50 mg/dL; where, LDL-C level will be measured directly by PUC.
2. LDL-C will be calculated using the Martin-Hopkins equation unless triglycerides ≥ 400 mg/dL or LDL-C ≤ 50 mg/dL; where, LDL-C level will be measured directly by PUC.

Primary Estimand

To assess the primary efficacy endpoint, the primary estimand is defined by the following key attributes:

- **Treatment:** obicetrapib versus placebo
- **Target Population:** participants who are randomized into the study
- **Analysis Population:** The ITT Population
- **Intercurrent events:** treatment discontinuation, prohibited medication use

- **Analysis set and handling of intercurrent events:** Treatment policy strategy will be used. All available values of LDL-C at Baseline and Day 84 will be included in the calculation of the percentage change from Baseline to Day 84.
- **Population level summary:** The difference in LS mean percentage change in LDL-C from Baseline to Day 84 between treatment groups

The analysis of covariance (ANCOVA) model with a fixed effect for the treatment group and covariates of Baseline LDL-C will be used to analyze the primary efficacy endpoint. The least squares (LS) mean, standard errors, and 2-sided 95% confidence intervals for each treatment group and for the mean difference compared to placebo will be estimated. The model will be fit assuming unequal variances for each treatment group. If substantial deviations from the model assumptions are observed, then supportive analyses, such non-parametric assessments, will be considered.

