- **Analysis set and handling of intercurrent events:** A hypothetical strategy will be used. All available values of LDL-C at Baseline and Day 84 will be included in the calculation of the percentage change from Baseline to Day 84.
- **Population level summary:** The difference in LS mean percentage change in LDL-C from Baseline to Day 84 between treatment groups.

This hypothetical estimand represents the treatment effect of obicetrapib relative to placebo at Day 84 in the randomized participants had they remained on their randomized treatment for the entire planned treatment period. This estimand uses a hypothetical strategy to handle intercurrent events and is intended to provide an estimation of the achievable study treatment effect if participants take the treatment as planned. The resulting missing values (corresponding to unobserved values or excluded values following study drug discontinuation or the use of prohibited medication) will be implicitly handled by using a MMRM approach under the assumption of missing at random. The model will be similar to the MMRM approach described previously for the supplemental analysis of the primary efficacy endpoint. The supplementary analysis for the primary efficacy endpoint assessed by secondary estimand will be performed using the mITT On-Treatment populations.

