3.4.4 Subgroup Analysis

The primary efficacy endpoint also will be analyzed by the following subgroups:

- Age categories (<65 years, 65 to 74 years, and 75+ years)
- Sex (male, female)
- Race (white, Asian, Black or African American, Other)
- Ethnicity (Hispanic/Latino, Not Hispanic/Latino)
- BMI (<25 kg/m², 25 -30 kg/m², ≥30 kg/m²)
- Region (North America and EMEA (Europe, Middle East, and Africa))
- Diabetes (yes, no)
- HDL-C (<40mg/dL, 40 - <60 mg/dL, ≥60mg/dL)
- ApoB (<60mg/dL, 60 - <90 mg/dL, ≥90mg/dL)
- ApoA1 (<110 mg/dL, ≥110 and <125 mg/dL, ≥125mg/dL)
- Lipoprotein(a) (<75nmol/L, ≥75 and <125 nmol/L, ≥125nmol/L)
- Non-HDL-C (<100 mg/dL, ≥100 and <130 mg/dL, ≥130mg/dL)
- LDL-C (<70mg/dL, ≥70 and <100 mg/dL, ≥100mg/dL)
- TG (<150 mg/dL, ≥150mg/dL)
- HbA1c (<5.7%, ≥5.75 to ≤6.4%, >6.4%)
- Urinary albumin:creatinine ratio (normal, micro-albuminuria, macro-albuminuria)
- eGFR (<60ml/min/1.73 m², ≥60 to <90ml/min/1.73 m², ≥90ml/min/1.73 m²)
- Statin treatment (high dose, low or moderate dose, none)
- Ezetimibe use (yes, no)
- Hs-CRP (<2mg/dL, ≥2mg/dL)
- HeFH (Genotyping confirmed or DLCN>8 points of Simon Broome definite; Simon Broome possible FH diagnosis)

The ANCOVA model with fixed effects for the treatment group, subgroup variable, treatment-by-subgroup variable and covariates of Baseline LDL-C will be used. The least squares (LS) mean, standard errors, and 2-sided 95% confidence intervals for each treatment group and for the mean difference compared to placebo, within each level of the subgroup, will be estimated. No imputation of missing data will be performed; therefore, the subgroup analysis will be performed

using only observed data. For the primary efficacy endpoint, the LDL-C values measured by PUC will be used. However, if the analysis for the primary efficacy endpoint specified above will show a difference between the 3 LDL-C approaches, then Friedewald and Martin-Hopkins equations may be considered for subgroup analysis.

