6 CHANGES FROM PROTOCOL-SPECIFIED STATISTICAL ANALYSES

There have been four changes from the protocol v3.0.

The first change is in the description of the study objectives and endpoints, the term 'fasting' from version 3.0 of the protocol, which precedes the specified lipid parameter, has been removed. The Schedule of Procedures, along with Section 8.7 of the protocol, specifies that all laboratory samples should be collected while the participant is fasting; therefore, the corresponding language was removed from the objective and endpoint descriptions in the SAP. Additionally, the primary efficacy endpoint for the LDL-C assessment will utilize values collected via preparative ultracentrifugation (PUC), also referred to as beta quantification, which is not sensitive to fasting status.

The second change is the inclusion of subgroup analysis.

The third change is the inclusion of the evaluation of trough levels of obicetrapib from Baseline to Day 84 and 180 in the obicetrapib group.

The fourth change is the change in the variance for the primary analysis. The model will assume unequal variances for each treatment group. Therefore, supportive analysis of the primary efficacy assessment will not require consideration of an ANCOVA model assuming unequal variances, as described in v3.0 of the protocol.

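### The primary ANCOVA lets the variance differ by arm but the MMRM of the same endpoint does not; under 2:1 allocation the MMRM's intervals are miscalibrated if the arm SDs differ, in a direction the documents do not settle

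*SAP*

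**What the plan says.** **Primary ANCOVA (SAP 3.4.1).** "The model will be fit assuming unequal variances for each treatment group". The sample code puts `group=TREATMENT` on the REPEATED statement and asks for Satterthwaite degrees of freedom. SAP Section 6 lists this as the fourth change from the protocol: "The model will assume unequal variances for each treatment group". Protocol 9.2.1.1 had an unequal-variance ANCOVA only as a possible supportive analysis.

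**Supplemental MMRM (SAP 3.4.1).** "The restricted maximum likelihood estimation approach will be used with an unstructured covariance matrix". The sample code reads "Repeated VISIT / TYPE=UN sub=USUBJID", with no `group=` option and no empirical variance option. The model uses ultracentrifugation (PUC) LDL-C and lists all visits to Day 365. Standard errors and 95% intervals are to be reported for the treatment group and for the comparison with placebo.

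**Hypothetical estimand (SAP 3.4.1, Secondary Estimand).** "The model will be similar to the MMRM approach described previously for the supplemental analysis of the primary efficacy endpoint". It has no other covariance statement and no code of its own.

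**Design (SAP 2.2).** "Approximately 300 eligible participants will be randomized in a 2:1 ratio". "Assuming an approximate 5% drop out rate, approximately 285 participants will be evaluable for efficacy".

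**When PUC is measured (Protocol 7.1).** PUC is done in all participants at Baseline, Day 84 and Day 365/EOT/ET. At the other scheduled visits it is done only if TG is at least 400 mg/dL or LDL-C is at most 50 mg/dL. SAP 3.4.2 confirms this for Day 180.

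**The concern.** `TYPE=UN` lets variances and correlations differ between visits. It does not let them differ between arms; that needs `group=TREATMENT`, which the SAP uses in the ANCOVA and omits in the MMRM. No reason is given for treating the same outcome differently in the two models.

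With equal allocation the omission would hardly matter for the treatment difference. With 2:1 allocation the pooled variance is dominated by the larger arm, while the sampling error of the difference depends more on the smaller one. The standard error is then wrong whenever the arm variances differ.

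Two uses are at stake. The MMRM is the only stated estimator for the hypothetical estimand. It is also the first supplemental check on the primary result, so a difference in interval width between it and the ANCOVA could reflect the variance assumption as well as the handling of missing data.

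**Working it through.** **Inputs.** Evaluable participants: 285 (SAP 2.2.2), split 2:1 into n1 = 190 obicetrapib and n0 = 95 placebo. Planned difference 30 points; SD 15 (SAP 2.2.2). The SAP gives no arm-specific SDs, so the ratios below are assumptions, with the placebo SD held at 15.

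**The plan's own figure.** 300 × 0.95 = 285. With SD 15 in both arms, SE = √[225 × (1/190 + 1/95)] = 1.885, and 30/1.885 = 15.9. Power is essentially 100%, so the stated figure of more than 90% holds.

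**Formulas for the Day 84 difference**, treating Day 84 data as nearly complete:

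- True SE² = s1²/190 + s0²/95
- Pooled SE² = [(189·s1² + 94·s0²)/283] × (1/190 + 1/95)
- Coverage of a nominal 95% interval = 2Φ(1.96 × pooled SE/true SE) − 1

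**Worked case, ratio 0.70 (s1 = 10.5, s0 = 15).** Pooled variance = (189 × 110.25 + 94 × 225)/283 = 148.4. Pooled SE = √(148.4 × 3/190) = 1.531. True SE = √(110.25/190 + 225/95) = 1.717. Ratio = 0.891.

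| Obicetrapib/placebo SD | Pooled SE/true SE | 95% half-width, pooled vs true | Coverage |
|---|---|---|---|
| 8.25/15 (0.55) | 0.834 | 2.70 vs 3.24 | 89.8% |
| 10.5/15 (0.70) | 0.891 | 3.00 vs 3.37 | 91.9% |
| 15/15 (1.00) | 1.000 | 3.69 vs 3.69 | 95.0% |
| 22.5/15 (1.50) | 1.138 | 5.00 vs 4.40 | 97.4% |

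**Where the ratios come from.** If spread scales with the level reached, the ratio is 1 − reduction: 0.70 at the planned 30%. At the 45.4% reduction in Protocol 1.4 it is about 0.55, but that study was in mild dyslipidemia. A ratio above 1 would arise if response to obicetrapib is heterogeneous, for example through mixed adherence.

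**Role of 2:1.** With n per arm, pooled SE² is [(s1² + s0²)/2] × (2/n) = s1²/n + s0²/n, which is the true value. The error in the difference therefore comes from the unequal allocation.

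**Per-arm LS means.** Here the error does not depend on allocation in the same way: each interval uses the pooled SD (√148.4 = 12.18 at ratio 0.70) in place of the arm's own.

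- Ratio 0.70: coverage about 98% for obicetrapib (12.18/10.5 = 1.16) and about 89% for placebo (12.18/15 = 0.81).
- Ratio 1.5: 92.3% for obicetrapib and 99.2% for placebo.

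**Check by simulation.** Full MMRMs were simulated with 1,500 trials per scenario, five visits, within-subject correlation 0.6 and 5% monotone dropout. Pooled coverage was 98.0% at SDs 22.5/15 and 91.1% at 15/22.5. By-arm covariance gave 94.6% to 95.3% in every scenario run, and point estimates stayed near −30. This supports the arithmetic, but it does not mimic the PUC schedule.

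**Effect on significance.** Over all SD pairs examined, out to a twofold difference either way (15/30 and 30/15), 30 points is at least 9.2 standard errors on either SE.

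**The case against.** The strongest reply is that a supplemental model may make different assumptions. A reader might infer that the SAP adopted arm-specific variances for LDL-C percent change generally and then broke its own rule. The documents do not go that far: Section 6 confines the change to the primary analysis. What stands is an unexplained inconsistency between two models of one endpoint.

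The MMRM code is labelled as sample code, and SAP Section 7 defers programming detail to a separate document. For the hypothetical estimand, pooling is inferred from the cross-reference. Both points are fair. Still, the text specifies one unstructured matrix and nothing on the page allows for arms to differ.

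The mixing of variance and missing-data assumptions is limited. The observed-case and tipping-point analyses keep the primary ANCOVA model, so missing-data handling can be compared with the variance model held fixed. That weakens the interpretive concern but does not correct the MMRM intervals themselves.

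Some stronger readings are tempting but unsupported:

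- A reader might infer that the MMRM intervals are simply wrong, or too narrow. With one SD in the documents, they may be too narrow, too wide or correct.
- A reader might infer that the subgroup ANCOVA in 3.4.4 also pools variances. The text is silent there and shows no code.
- A reader might count the missing degrees-of-freedom option as a separate error. At about 285 participants the multiplier is 1.968 against 1.960, which is trivial.

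Finally, simply adding by-arm covariance over five visits could fail. Entry required LDL-C of at least 70 and TG below 400 mg/dL at Screening (Protocol 4.1), so few placebo participants can be expected to have PUC values at Days 30, 180 and 270. This objection stands and shapes the fix.

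**Conclusion.** The point holds as a specification inconsistency with a bounded consequence. If the arm SDs differ, the supplemental MMRM, and by cross-reference the hypothetical-estimand MMRM, give a miscalibrated standard error and 95% interval for the difference, and miscalibrated per-arm intervals. At assumed SD ratios of 0.70 and 1.5 the SE of the difference is 11% too small or 14% too large, with coverage of about 92% or 97%. At equal SDs nothing changes. These sizes rest on a 190:95 split, a placebo SD of 15, nearly complete Day 84 data and ratios that the documents do not supply.

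A reader might infer a threat to the trial's main conclusion. There is none: the primary ANCOVA already has arm-specific variances, the sequential tests in SAP 3.4.2 use similar ANCOVA models, and neither MMRM is in that sequence. At the planned effect significance would not change. What is affected is the accuracy of the reported MMRM intervals and how cleanly they compare with the primary analysis.

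**What to change.** In SAP 3.4.1, before unblinding:

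- Add `group=TREATMENT` to the REPEATED statement of the MMRM and state the degrees-of-freedom method (Kenward-Roger, or Satterthwaite as in the primary code).
- Restrict the model to Days 84 and 365, the post-Baseline visits where PUC LDL-C is measured in all participants.
- Name a fallback if the model does not converge: a simpler by-arm structure or an empirical sandwich variance.
- State that the hypothetical-estimand MMRM uses the same specification.

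The cost is SAP wording and a small code change. A two-visit unstructured matrix has 3 parameters, so by-arm fitting needs 6: three more than a pooled two-visit model, and fewer than the 15 of a single five-visit matrix. The real downside is that Days 30, 180 and 270 leave the model. That includes any Day 30 information on participants who stop treatment before Day 84, but under the PUC rule such values would exist only for a selected few.
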